3.3. Disposition

The number and percentage of subjects completing or prematurely discontinuing the study including reasons for discontinuation will be summarized for the following:

- Subjects who enrolled in the study
- Subjects in the Safety Population
- Subjects who completed the treatment period
- Subjects who discontinued treatment along with reason for discontinuation
- Subjects who are ongoing in the treatment period

3.4. Demographics and Baseline Characteristics

Demographics and baseline characteristics such as sex, age, race, ethnicity, weight, and body mass index (BMI) will be summarized for the Safety Population.

3.5. Prior and Concomitant Medication

Prior medications will be defined as medications taken prior to the first dose of study drug in ALK3831-A308 study. Concomitant medications will be defined as medications taken on or after the first dose of study drug in ALK3831-A308 study. All medications will be coded using the World Health Organization WHO-DD Enhanced + Herbal (version: March 2016).

Concomitant medications taken during the treatment period will be summarized by the preferred name, for the Safety Population. All reported medications (including those initiated after the last dose of study medication) will be included in the listing. For the summary table, if a subject has taken a concomitant medication more than once, the subject will be counted only once for that medication.

3.6. Treatment Adherence Rate and Extent of Exposure to Study Drug

3.6.1. Treatment Adherence Rate

Treatment adherence to the daily dosing schedule during treatment period will be summarized. Treatment adherence will be calculated as follows:

$$100 \times \frac{\text{Total tablets dispensed} - \text{total tablets returned} - \text{total tablets lost}}{\text{Total tablets scheduled to be taken}}$$

3.6.2. Extent of Exposure to Study Drug

Duration of exposure to study drug (ALKS 3831) is defined as the number of days from the date of the first dose of study drug in this study (ALK3831-A308) to the date of the last dose of study drug, inclusive (ie, last dose date – first dose date + 1 day). Duration of exposure to study drug will be summarized for the Safety Population.

The overall mean and modal dose of olanzapine will be summarized. Number and percentage of subjects will be summarized by their modal dose level and final dose level. Summary of the

extent of exposure will also be presented by demographic subgroups: Age, Sex, Race, Region, weight, and body mass index (BMI). Dose level will be summarized by visit at 12 months, 18 months, 24 months, and 48 months.

Dose level at 12 months, 18 months 24 months, and 48 months will be summarized by antecedent study.

3.7. Efficacy Analyses

3.7.1. Efficacy Analysis

The following efficacy endpoints will be analyzed:

- Change from baseline in CGI-S score by visit
- Shift analysis in CGI-S
- Change from baseline in IWQOL-Lite scales (total score, physical function, self-esteem, sexual life, public distress, and work) by visit
- Time to treatment discontinuation

Value and change from baseline in CGI-S and IWQOL-Lite scores by visit will be summarized using descriptive statistics.

The IWQOL-Lite scale is a 31-item self-report measure of obesity-specific quality of life. IWQOL-Lite provides an overall total score as well as scores on five domains: (1) physical function, (2) self-esteem, (3) sexual life, (4) public distress, and (5) work. The raw scores will be transformed as follows (Tessier et al, 2012): the transformed scores range from 0 to 100, with 100 representing the best, and 0 representing the most impaired quality of life.

$$\text{Transformed Score} = \frac{\text{maximum theoretical score} - \text{actual score}}{\text{test score range}} \times 100$$

CGI-S response will be categorized into the categories summarized in [Table 1](#). The number and percentage of subjects in each category and with shifts from baseline will be summarized based on the observed data by descriptive statistics at 1, 3, 6, and 12 months. The shift categories are summarized in [Table 2](#).

Table 1: Definition of Shift CGI-S Categories

Response Category	CGI-S Score
Markedly to Extremely Ill	≥ 5
Moderately Ill	4
Normal to Mildly Ill	≤ 3

Table 2: Shift Categories for CGI-S response

Shift from Baseline Category for CGI-S Response	
Baseline Category	Shift Category
Markedly to Extremely Ill	
No change	
≥ 1 level improvement	
2 level improvement	
Moderately Ill	
No change	
1 level improvement	
1 level worsening	
Normal to Mildly Ill	
No change	
≥ 1 level worsening	
2 level worsening	

Time to treatment discontinuation will be analyzed using the Kaplan-Meier method and the KM plot will be provided. Both all-cause discontinuation and discontinuation due to AE will be summarized. For prematurely discontinued subjects (all cause or due to AE), time to event is defined as time from the date of first dose of study drug in study ALK3831-A308 to the date of last dose of study drug. Other subjects will be censored at the last dose of the study drug.

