8. STUDY DESIGN

8.1. Overall Study Design and Plan

This is a multicenter, open-label study to evaluate the long term safety, tolerability, and durability of treatment effect of ALKS 3831 in subjects with schizophrenia, schizophreniform disorder, or bipolar I disorder. Subjects that have completed the antecedent studies (ALK3831-A304, ALK3831-A306, or ALK3831-A307) within the past 7 days will be eligible to enroll in this study.

[figure not shown]
Subjects enrolled in the study will be started on the same olanzapine dose that they had maintained at the end of the antecedent study. Available doses of ALKS 3831 will be 5/10, 10/10, 15/10, and 20/10 mg. Subjects may be titrated to a different dose after the start of the study at the Investigator's discretion. Dosing will be flexible throughout the study; however, frequent adjustments are discouraged. Dose adjustments will only be performed on-site at the study center. Subjects requiring dose adjustments between scheduled visits will need to arrange an unscheduled visit.

Safety assessments will include AE monitoring, clinical laboratory testing, vital signs, body weight, ECGs, and the Columbia-Suicide Severity Rating Scale (C-SSRS). Psychiatric symptoms will be evaluated using the CGI-S scale. Additional assessments will include Impact of Weight on Quality of Life-Lite Questionnaire (IWQOL-Lite).

The duration of the treatment period will vary by subject, between 24 and 48 months, or until regulatory action; duration will vary by subject. The study completion is targeted for the 4th quarter of 2022. After the last subject is enrolled, the end date of the study will be set to occur 24 months later (approximately the 4th quarter of 2022), and subjects will be informed of the target completion date. The total study duration will be up to 49 months including a treatment period of 24 to 48 months and a 4-week safety Follow-up period and return to their normal standard of care once their participation has ended. A schematic of the study design is provided in Figure 1.

The end of trial is defined as the date of the last subject's last visit.

Figure 1: Study Design Schematic

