3.7.3. Subgroup Analysis

Subgroup analyses of efficacy endpoints will be performed for each of the following categories:

- Bipolar disorder
 - Change from baseline in IWQOL-Lite score by visit
 - Weight, metabolic responses, waist circumference, safety AEs and shift in CGI score in 2 points or 5 compared to those hospitalized due to AEs will be presented by visit.
- Sex (male, female)
- Age (<18 years, ≥ 18 years)
- Age (<30 years, ≥ 30 years)
- Race (Black or African American, Non-Black or Non-African American)

- Baseline BMI (<25 kg/m², ≥25 kg/m²)
- Region (US, Non-US)
- Among those who completed study at 24 months, 36 months, and 48 months, change in weight, waist circumference and metabolic responses will be summarized.
- For those who switched from ALKS3831-A307 to ALKS3831-A308 change from baseline in CGI, weight, waist circumference and lipid levels by visit will be summarized.

Descriptive statistics will be provided for the subgroups listed above.

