4. INTERIM ANALYSES

As described in [Section 1](#), this SAP document is an update of the interim analysis that was conducted to support the ALKS 3831 New Drug Application (NDA). The full study population will be analyzed once the study is completed.

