5. CHANGES IN CONDUCT OR PLANNED ANALYSES FROM THE PROTOCOL

To further assess the long-term durability, the following analysis was added in ISAP but was not specified in protocol:

- Shift analysis in CGI-S

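### The CGI-S shift table was added to assess long-term durability but stops at Month 12, before 36 of the 48 scheduled postbaseline CGI-S visits

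*SAP*

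**What the plan says.** SAP section 3.7.1 groups CGI-S into three severity categories (its Table 1) and defines shifts from the baseline category (its Table 2). It sets the time points as follows: "shifts from baseline will be summarized based on the observed data by descriptive statistics at 1, 3, 6, and 12 months".

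SAP section 5 gives the reason for the analysis: "To further assess the long-term durability, the following analysis was added in ISAP but was not specified in protocol". The shift analysis in CGI-S is the only item listed there.

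The planned duration in Protocol section 8.1 is "between 24 and 48 months, or until regulatory action", and durability of treatment effect is part of the primary objective (Protocol 6.1, SAP 1.1.1). SAP section 4 says of the final analysis: "The full study population will be analyzed once the study is completed".

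The SAP reports other quantities later than Month 12:

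- CGI-S as a score (3.7.1): "Value and change from baseline in CGI-S and IWQOL-Lite scores by visit will be summarized using descriptive statistics".
- Dose (3.6.2): "Dose level will be summarized by visit at 12 months, 18 months, 24 months, and 48 months".
- Completers (3.7.3): "Among those who completed study at 24 months, 36 months, and 48 months, change in weight, waist circumference and metabolic responses will be summarized".
- The bipolar subgroup only (3.7.3): "shift in CGI score in 2 points or 5 compared to those hospitalized due to AEs will be presented by visit".

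**The concern.** The purpose of the table and its time points do not match. A table meant to inform long-term durability describes category change only in the first 12 study months of a treatment period planned to last at least twice that, unless regulatory action ends it sooner. The final analysis will have the later ratings, and the SAP gives no reason for leaving them out.

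The by-visit score summaries do not replace the table. They give n, mean, SD, median, minimum and maximum, and they do not count subjects by severity category or by shift from baseline category. For illustration, if equal numbers of subjects improve and worsen by two points, the mean change is zero even though some subjects have lost their response. The shift table is the planned output that would show this, and after Month 12 it is absent for the population as a whole.

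**Working it through.** **Inputs**

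- Shift time points: Months 1, 3, 6 and 12 (SAP 3.7.1).
- CGI-S analysis visits: Visits 2 to 49 (SAP 6.1, Table 10), with a month defined as 28 days.
- Planned treatment: 24 to 48 months, or until regulatory action (Protocol 8.1 and Table 3).

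**Reproducing Table 10.** Visit v is Month v − 1, with target day 28 × (v − 1) + 1.

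- Visit 13, Month 12: 28 × 12 + 1 = Day 337. This matches.
- Visit 25, Month 24: 28 × 24 + 1 = Day 673. This matches.
- Visit 49, Month 48: 28 × 48 + 1 = Day 1345. This matches.

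**Share of the schedule after the last shift time point**

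| | Treated to Month 48 | Treated to Month 24 |
|---|---|---|
| Postbaseline CGI-S visits | 49 − 2 + 1 = 48 | 25 − 2 + 1 = 24 |
| Visits after Visit 13 | 49 − 13 = 36 | 25 − 13 = 12 |
| Share of visits | 36/48 = 75% | 12/24 = 50% |
| Days after Day 337 | 1345 − 337 = 1008 | 673 − 337 = 336 |
| Share of days after Day 1 | 1008/1344 = 75% | 336/672 = 50% |

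**Cross-check.** Protocol Table 3 schedules CGI-S at 32 monthly visits, 15 quarterly visits and the end-of-treatment visit (no later than Visit 49): 32 + 15 + 1 = 48. These are the same visits, and 36 of them come after Visit 13. The safety follow-up visit also collects CGI-S, but Table 10 does not map it, so it is not counted.

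**Does another output fill the gap?**

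- By-visit CGI-S value and change (3.7.1) run to Month 48, without counts by category.
- Kaplan-Meier time to discontinuation, disposition by reason and the SAE tables cover the whole period. They do not show the severity category of subjects who stay on treatment.
- Early-termination ratings go into the by-visit summaries if they can be mapped, and otherwise into listings.
- The bipolar item in 3.7.3 covers one subgroup, does not cite the Table 1 and Table 2 categories, and is unclear as worded.
- The item in 3.7.3 for subjects entering from study A307 gives change in CGI by visit, not shifts, and again for one subgroup.

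None of these gives whole-population category shifts after Month 12. Other categorical summaries have no such limit: BMI shifts (3.7.4) and weight gain of at least 7% or 10% (3.8.3.2) are both planned by visit.

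**The case against.** The strongest case on the other side concerns weight, not fact. The protocol's own CGI-S endpoint is change from baseline by visit, and the SAP keeps that to Month 48. Time to discontinuation also spans the whole treatment period. The shift table is an addition outside the protocol, in a single-arm descriptive study with no formal sample size and no multiplicity plan. Its time points could be called a matter of preference. This stands to the extent that no estimate, error rate or protocol endpoint is affected.

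The 75% figure assumes a subject followed to Month 48. Protocol 8.1 sets the end of the study 24 months after the last enrolment, so late enrollees cannot get that far. For them 50% is the relevant figure. That is why both are given.

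Observed-data shifts at Months 36 and 48 describe only subjects still being rated, and could make durability look better than it is. This also stands. Showing n exposes the selection but does not correct it. The same limit already applies to the by-visit CGI-S summaries and to the existing shift columns, so it is not a reason to leave the later ones out.

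Finally, the interim SAP and the mock tables are not available here, so the reason for stopping at Month 12 is unknown. It may have been carried over from the interim analysis, but the documents do not say so. A stated reason would also reconcile 3.7.1 with section 5, though the later category counts would then still be missing.

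**Conclusion.** The concern holds. The CGI-S shift table has no time point after Month 12 (Day 337). That leaves out 36 of 48 scheduled postbaseline CGI-S visits (75%) for a subject treated to Month 48, and 12 of 24 (50%) for one treated to Month 24. These figures rest on the Table 10 schedule and say nothing about how many subjects or ratings are affected, because the documents do not give the number on treatment at each visit.

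The consequence is limited. A supplementary descriptive table does not cover the period it was added to inform, while mean CGI-S and discontinuation are still reported. The change should be made because it is cheap and lets the table serve its stated purpose.

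**What to change.** In SAP 3.7.1, extend the shift time points to Months 1, 3, 6, 12, 18, 24, 36 and 48, and state that n will be shown at each. The four additions are Visits 19, 25, 37 and 49 (Days 505, 673, 1009 and 1345). All four months already appear in 3.6.2 or 3.7.3.

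An optional second step is a column for the last postbaseline value as defined in SAP 6.1, shown with time on treatment. It captures subjects who worsened and left only if they have a rating, and it mixes follow-up times, so it supports the fixed-month columns and does not replace them.

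The cost is one wording change and four more time points in an existing table (five columns with the optional one), using data already collected. The downside is few and selected subjects at the late visits, so the percentages there must be read with n.

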7.3. Subject Withdrawal

A subject may be discontinued from the study at any time if the subject, Investigator, or Sponsor determines that it is not in the best interest of the subject to continue participation. If a subject has an absolute neutrophil count (ANC) $< 1.0 \times 10^3$ per μ L or Hemoglobin A1c (HbA1c) $\ge 6.5\%$ at any time, the PI (or designee) should discontinue the subject from participation immediately. Reasons for discontinuation include:

- Adverse Event
- Lack of Efficacy
- Lost to Follow-up
- Withdrawal by Subject
- Protocol Deviation (including non-compliance with study drug or study procedures)
- Pregnancy
- Study Terminated by Sponsor
- Other

If a subject withdraws from the study for any reason, any ongoing AEs will be followed until resolution, until deemed stable by the Investigator, or until the subject is deemed by the Investigator to be lost to follow-up. If, in the opinion of the Investigator, it is necessary to monitor a subject beyond the safety follow-up visit, the follow-up period may be extended as necessary. In such instances, the Sponsor and Investigator will agree to an acceptable follow-up schedule.

In the event that a subject chooses to withdraw from the study, the Investigator should make a reasonable effort to ascertain the reason(s) for withdrawal, while fully respecting the subject's rights. Subjects who terminate the treatment early (prior to Visit 25) will complete an early termination (ET) visit and the 4-week Safety Follow-up period. The ET visit should be scheduled as close as possible to the subject's last dose and will mimic the assessments scheduled to be conducted at the EOT Visit. If the subject fails or refuses to return to the study center, an attempt must be made to contact the subject by telephone in order to assess as many safety and efficacy parameters as possible. All data collected over the telephone must be documented and kept in the subject's record.

The Investigator must maintain a record of all subjects who fail to complete the study. The reason for study discontinuation will be documented and made on the appropriate electronic case report form (eCRF). If a subject is lost to follow-up, a reasonable attempt to contact the subject must be made and documented.

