3.8.1.1. Deaths, Serious and Other Significant AEs

The number and percentage of subjects who have serious adverse events (SAE) and AEs leading to discontinuation from the treatment will be summarized by system organ class and preferred term. And the number and percentage of subjects reporting SAEs will be summarized by system organ class, preferred term, and relationship to study drug.

By-subject listings will be provided for SAEs, AEs leading to treatment discontinuation and AEs leading to death.

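### Kaplan-Meier for discontinuation due to AE censors stops for other reasons, so 1-KM overstates the proportion who stop for an AE; no cumulative incidence function is planned

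*SAP*

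**What the plan says.** SAP 3.7.1 (Efficacy Analysis) names the estimator: "Time to treatment discontinuation will be analyzed using the Kaplan-Meier method and the KM plot will be provided". It names two events: "Both all-cause discontinuation and discontinuation due to AE will be summarized". Event time runs from first to last dose in this study for subjects with the event. For everyone else the rule is: "Other subjects will be censored at the last dose of the study drug".

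Protocol 7.3 lists the reasons for discontinuation: AE, lack of efficacy, loss to follow-up, withdrawal by subject, protocol deviation, pregnancy, "Study Terminated by Sponsor" and other.

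Two crude summaries are also planned. SAP 3.3 counts "Subjects who discontinued treatment along with reason for discontinuation", and under SAP 3.8.1.1 "AEs leading to discontinuation from the treatment will be summarized by system organ class and preferred term". On follow-up, Protocol 8.1 says: "The duration of the treatment period will vary by subject, between 24 and 48 months, or until regulatory action".

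Neither document mentions competing risks or a cumulative incidence function. Protocol 14.4 specifies Kaplan-Meier for time to discontinuation and has no cause-specific version.

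**The concern.** When the event is discontinuation due to AE, the subjects described as other are everyone who did not stop for an AE: completers, and those who stopped for another reason. Censoring completers is right, because their follow-up ended administratively. Censoring the second group is different. A subject already off study drug cannot later discontinue it for an AE, yet Kaplan-Meier gives that subject the future AE-stop risk of those still on treatment. The complement of the curve then exceeds the proportion who actually stop for an AE, and the gap cannot shrink as follow-up lengthens.

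The primary objective is long-term safety, tolerability and durability of effect. This curve is the only planned description of AE discontinuation over time, and a reader will naturally take from it the proportion stopping for an AE by Month 24, 36 or 48. It is least accurate at the longest follow-up, the period the extension was set up to describe.

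The crude percentages do not carry this inflation. But treatment length differs between subjects, so they do not give the risk by a stated time.

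**Working it through.** **Direction.** Let h_AE(t) be the hazard of stopping for an AE, S_all(t) the probability of no stop for any reason, and S_AE(t) the Kaplan-Meier quantity that counts AE stops only.

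- The true cumulative incidence (CIF) grows by S_all(t-) × h_AE(t).
- 1-KM grows by S_AE(t-) × h_AE(t).
- S_AE is never below S_all, so 1-KM is never below the CIF. It is strictly above once an AE stop follows a non-AE stop. The difference grows by (S_AE − S_all) × h_AE, which is never negative.

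**Inputs for size.** The plan states no discontinuation rate and no formal sample size, so there is no figure of its own to reproduce. Assumed: F48, all-cause discontinuation by Month 48, and s, the AE share of stops. From the documents: about 500 subjects and treatment of 24 to 48 months.

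**Constant hazards.** F(t) = 1 − (1 − F48)^(t/48); CIF(t) = s × F(t); 1-KM(t) = 1 − (1 − F(t))^s.

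With F48 = 0.60 and s = 0.20:

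| Month | F(t) | CIF = 0.2 × F | 1-KM = 1 − 0.4^(0.2t/48) | Excess |
|---|---|---|---|---|
| 12 | 20.5% | 4.1% | 4.5% | 0.4 points |
| 24 | 36.8% | 7.4% | 8.8% | 1.4 points |
| 36 | 49.7% | 9.9% | 12.8% | 2.9 points |
| 48 | 60.0% | 12.0% | 16.7% | 4.7 points |

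Range of the ratio at Month 48, for F48 of 40-70% and s of 10-30%:

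- Lowest (F48 = 0.40, s = 0.30): 1 − 0.6^0.3 = 14.2% against 12.0%, ratio 1.18.
- Highest (F48 = 0.70, s = 0.10): 1 − 0.3^0.1 = 11.3% against 7.0%, ratio 1.62.

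**Fewer competing stops.** Fix the true Month 48 AE incidence at 10% and let O be the proportion stopping for other reasons: 1-KM = 1 − (0.90 − O)^(0.10/(0.10 + O)). O = 10% gives 10.6%, O = 40% gives 12.9% and O = 60% gives 15.8%. The problem is small if other-cause stops are rare.

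**AE hazard not constant.** Keep the total hazard constant and scale the AE hazard so that CIF(48) = 0.2 × F48. For F48 = 0.60 (CIF 12.0%), an AE hazard proportional to exp(−t/12) gives 1-KM of 13.6%, and one proportional to 0.5 + t/48 gives 18.0%. Across F48 of 40-70% the ratio is 1.07 to 1.18 when AE stops come early and 1.26 to 1.67 when they come late.

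**Staggered closure.** Simulation of 500 subjects with planned end of treatment uniform over Months 24-48, F48 = 0.60, s = 0.20, read at Month 46:

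- 1-KM: 16.1%.
- Aalen-Johansen: 11.7%, equal to the true value 0.2 × (1 − 0.4^(46/48)) = 11.7%.
- Crude end-of-study percentage: about 9.9%. In expectation this is the average of 0.2 × F(c) over closure times c: 0.2 × [1 − (0.4^0.5 − 0.4)/(0.5 × 0.916)], where 0.916 = −ln 0.4.

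The two planned summaries would thus show about 16% and about 10%, and neither is the proportion stopping for an AE by that time.

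**The case against.** The best case against acting has four parts.

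- **Target.** The SAP never says that the curve's complement is the proportion stopping for an AE, and it sets no landmark months for this analysis. Cause-specific Kaplan-Meier could be defended as describing a setting in which no one stops for another reason. It is true that the SAP does not name its target. But the hypothetical reading needs other-cause stops to be independent of AE risk, which the SAP does not claim, and that setting is of little interest in a tolerability study.
- **Precision.** In the staggered-closure example the excess at Months 24, 36 and 46 is 1.4, 2.9 and 4.4 points. The Kaplan-Meier standard errors are about 1.4, just under 2 and about 3 points, with roughly 316, 125 and 17 subjects at risk. Late figures are therefore imprecise as well as biased, and Month 24 is the fairer headline. Imprecision does not excuse a systematic error that a standard method removes.
- **Definition of premature.** Protocol 7.3 ties early termination to stopping before Visit 25 (Month 24), while treatment can run to Visit 49. If the SAP's premature discontinuation means before Visit 25, the AE curve is flat after Month 24 and the later figures above do not arise. The SAP does not settle this.
- **Consequence.** The study is single-arm and descriptive, AE-specific discontinuation is not a protocol endpoint, the error exaggerates AE stops rather than hiding them, and uninflated counts and listings are planned. All of this is correct. It limits the severity but does not make the curve right.

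**Conclusion.** The concern holds. As written, the rule treats stops for other reasons as non-informative censoring in the AE analysis, and 1-KM overstates the proportion who stop for an AE. The direction follows from algebra and needs no assumption about rates beyond some AE stops following other-cause stops.

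The size cannot be taken from the documents. In the central illustration it is modest at Month 24 (factor 1.19, from 8.76/7.35) and material at Month 48 (factor 1.40, from 16.74/12.00). Those figures assume constant hazards and that stops after Visit 25 count as events.

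This should be corrected, but it threatens no test or decision. The all-cause Kaplan-Meier is sound provided every subject-level withdrawal is an event and study closure is censored. The SAP leaves that last point unstated for stops recorded as sponsor termination. It is a secondary ambiguity and adds no weight to the main finding.

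**What to change.** In SAP 3.7.1, report discontinuation due to AE as an Aalen-Johansen cumulative incidence function. Make discontinuation for any other subject-level reason the competing event, and censor at completion or study closure. Keep Kaplan-Meier for all-cause discontinuation.

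In the same place, state that any subject-level stop before the subject's planned end of treatment is an event, including after Visit 25. State also that planned closure, regulatory action and stops recorded as sponsor termination are censored. Showing the number at risk under both curves would warn readers about the sparse late months.

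The cost is one or two sentences and one standard procedure. Discontinuation reasons and last-dose dates are already collected. The only downside is that the AE result is no longer a simple Kaplan-Meier curve.
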